- 4.A.12 Patients must have absolute neutrophil count (segmented neutrophils and bands) 1,500 /μL and platelets > 100,000/μL within 28 days prior to Cycle 1, Day 1 unless decreased counts have been shown to be due to marrow involvement with NHL.

NOTE: For progression to treatment with Zevalin: Patients must have < 25% bone marrow involvement with lymphoma as determined after cycle 2 of ESHAP. For patients without bone marrow involvement, there must be adequate bone marrow reserves as defined under EXCLUSION. (These criteria must be strictly met for adequate patient safety.)

Additionally, patients must have:

- serum creatinine value < 2.0 and total bilirubin < 2.0.
- Platelet counts $\geq 150,000/\text{mm}^3$, these patients will receive a dose of 0.4 mCi/kg of Zevalin
- Platelet counts from 100,000/mm³ to 149,000/mm³, these patients will receive a 0.3 mCi/kg dose of Zevalin
- 4.A.13 Patients with renal insufficiency or renal failure (serum creatinine > 2.0 mg/dL; creatinine clearance < 50 ml/min) are not eligible for this study. A serum creatinine or creatinine clearance must be obtained within 28 days prior to Cycle 1, Day 1.
- 4.A.14 Pregnant or nursing women may not participate. Women or men of reproductive potential must agree to use an effective contraceptive method as determined by the treating physician from the time of Cycle 1, Day 1 to 6 months after receiving the Zevalin.
- 4.A.15 No prior malignancy is allowed except for adequately treated basal cell or squamous cell skin cancer, in situ cervical cancer, or other cancer for which the patient has been disease-free for 5 years.
- 4.A.16 If Day 28 falls on a weekend or holiday, the limit may be extended to the next working day. In calculating days of tests and measurements, the day a test or measurement is done is considered Day 0. Therefore, if a test is done on a Monday, the Monday 4 weeks later would be considered Day 28. This allows for efficient patient scheduling without exceeding the guidelines.
- 4.A.17 All patients must be informed of the investigational nature of this study and give written informed consent in accordance with institutional and federal guidelines.
- 4.A.18 Expected survival \geq 3 months

4.B Exclusion Criteria

- 4.B.1 Patients with impaired bone marrow reserve, as indicated by one or more of the following:
 - Platelet count < 100,000 cells/mm³
 - Hypocellular bone marrow (cellularity < 10%)

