For the purpose of toxicity assessment, the treatment period will include the time from the first ESHAP infusion to 30 days following Zevalin infusion. Evaluations during the 2 cycles of ESHAP are outlined in Appendix A.

5.B.1 ESHAP Cycle 1, Day 1

a. Begin ESHAP Treatment (Please refer to Section 7A for ESHAP administration)

5.B.2 ESHAP Cycle 2, Day 1

- a. History & Physical examination, including vital signs (BP, temperature & pulse), height, weight, Body Surface Area (BSA), and performance status (Appendix B).
- b. Laboratory tests including:
 - Complete blood count (CBC) with differential and platelet count
 - Serum chemistries BUN, creatinine
- c. Toxicity Assessment: Adverse events are to be recorded on an ongoing basis and on appropriate source documents at the clinical site and in the patient's case report form.

5.B.3 ESHAP Cycle 2, Day 29

- a. History & Physical examination, including vital signs (BP, temperature & pulse), height, weight, Body Surface Area (BSA) & performance status (Appendix B).
- b. Laboratory tests including:
 - Complete blood count (CBC) with differential and platelet count
 - Serum chemistries BUN, creatinine
- c. Unilateral or Bi-lateral bone marrow biopsy and aspirate for histology and determination of percent bone marrow involvement
- d. Bone marrow cytogenetics. Does not have to be done at each Bone Marrow biopsy and aspirate, but does need to be completed at either, Baseline or Cycle 2, Day 29.
- e. Disease Assessment:
 - Total of all measurable indicator lesions.
 - CT or PET scan of the chest, abdomen and pelvis
- f. Toxicity Assessment: Adverse events are to be recorded on an ongoing basis and on appropriate source documents at the clinical site and in the patient's case report form.

5.C Evaluations During the Zevalin Imaging & Treatment Period

Ibritumomab Tiuxetan Indium (111 In Zevalin) regimen is administered 4 – 6 weeks after completion of ESHAP.

5.C.1 Day 1

- a. History & Physical examination, including vital signs (BP, temperature & pulse), height, weight, Body Surface Area (BSA), and performance status are to be performed within 28 days of Rituximab & Zevalin administration. (Appendix B).
- b. Toxicity Assessment: Adverse events are to be recorded on an ongoing basis and on appropriate source documents at the clinical site and in the patient's case report form.
- c. Laboratory tests including:
 - Complete blood count (CBC) with differential and platelet count
 - Serum chemistries BUN, creatinine

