undergoing DNA synthesis (S phase) and may also block cells from progressing to S phase from G1. Extensive chromosomal damage, including chromatid breaks, occurs. Ara-C appears to be most effective in tumors with high growth fraction.

b. TOXICOLOGY

Human Toxicology: Side effects of ara-C include myelosuppression, nausea, vomiting, diarrhea, anorexia, anal ulceration, stomatitis, rash, headache, fever, myalgia, malaise, bone pain, chest pain, hepatic and renal dysfunction, and alopecia. Central nervous system toxicity, i.e., signician cerebral and cerebellar dysfunction, progression to coma, has been seen with high doses. Severe cardiomyopathy has been reported with high dose ara-C in combination with cyclophosphamide. Progressive ascending paralysis has occurred in two patients receiving IV and intrathecal ara-C. Marked keratoconjuncitivitis has also occurred with high doses.

The most frequently reported reactions after intrathecal administration were nausea, vomiting and fever. Paraplegia and meningitis has been reported with intrathecal administration. Ara-C given intrathecally may cause systemic toxicity and careful monitoring of the hemopoietic system is indicated. If used intrathecally of if high dose therapy is used, do not use a diluent containing benzyl alcohol.

Ara-c can cause fetal harm when administered to a pregnant woman, however, there are no adequate and well-controlled studies in pregnant women.

c. PHARMACOLOGY

Kinetics: Ara-C is metabolized by deoxycytidine kinase and related kinases to nucleotide triphosphate, which is an active inhibitor of DNA polymerase. Deoxyccytidine prevents or delays cytotoxic activity. The active form is converted to nontoxic uracil derivatives by pyrimidine nucleoside deaminases. The balance of kinase and deaminase levels appears to be an important factor in sensitivity/resistance of the cell to ara-C. After IV injection, plasma disappearance of ara-C is biphasic. Initial half-life is 10 minutes, delayed half-life if 1-3 hours. After 24 hours, 80% is excreted in the urine as its inactive metabolite, ara-U. After a single IV administration of ara-C, levels in CSF are low. With intrathecal administration, half-life is 2 hours. There is little conversion to ara-U because of low CSF levels of diaminase. Drug interaction of ara-C has been reported with digoxin, gentamycin and fluorocytocine.

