7 TREATMENT PLAN

All patients who qualify for this study will receive chemotherapy with ESHAP followed by treatment with Zevalin

7.A ESHAP REGIMEN DOSING

ESHAP chemotherapy: Patients will receive 2 cycles of cytoreductive chemotherapy according to the schedule described below. (Table 7)

TABLE 7 ESHAP CHEMOTHERAPY PLUS ZEVALIN

DRUG	DOSE	ROUTE	DAYS	INTERVAL
Etoposide	$40 \text{ mg/m}^{2/} \text{day}$	IV infusion over 1 hour	1,2,3,4	q 28 days for 2 cycles
Methylprednisolone	250 mg/day	IV push	1,2,3,4	q 28 days for 2 cycles
		_		
Cytarabine	2000 mg/m^2	IV infusion over 2 hours	4	q 28 days for 2 cycles
Cisplatin	25 mg/m ² /day	IV infusion at 1mg/min	1,2,3,4	q 28 days for 2 cycles

- The cycle length will be 28 days if bone marrow recovery allows. If recovery requires an additional week, then the second cycle will be postponed for a week.
- Either pegfilgastrim or filgastrim may be given at the investigator's discretion.

7.B RITUXIMAB, 111 IN ZEVALIN, AND 90 Y ZEVALIN ADMINISTRATION

The rituximab + ibritumomab tiuxetan regimen is given 4-6 weeks after completion of the second cycle of ESHAP. Treatment can be completed within 7 - 9 days in an outpatient setting

TABLE 8
Rituximab, 111In Zevalin, AND 90Y Zevalin Administration

AGENT	DOSE	ROUTE	DAYS	NOTES
Rituximab	250 mg/m ²	Slow IV	1, then 7, 8 or 9	Give prior to 111 In Zevalin
¹¹¹ In Zevalin	5 mCi	Slow IV push over 10 minutes	1	Give within 4 hours after rituximab
⁹⁰ Y Zevalin	Depends on platelet count (see Section 7.B.3)	Slow IV push over 10 minutes	7, 8, or 9	Give within 4 hours after rituximab

7.B.1 Rituxan & 111 In Zevalin Administration

1.6 mg of ¹¹¹In Zevalin (5.0 mCi of ¹¹¹In) will be used for radioimaging. The imaging dose of ¹¹¹In Zevalin will be administered by a 10-minute slow IV push injection immediately following the infusion of Rituxan. ¹¹¹In Zevalin may be directly injected by stopping the flow from the IV bag and injecting the radiolabeled antibody directly into the line. A 0.22 micron filter must be on line between the patient and the infusion port. Flush the line with at least 10 mL of normal saline after ¹¹¹In Zevalin has been injected. (See Appendix H).

a. Oral premedication (2 tablets [325 mg] of acetaminophen and 50 - 100 mg oral diphenhydramine hydrochloride) may be administered 30 - 60 minutes prior to starting each infusion of rituximab.

7.B.2 Radioimaging Schedule

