8 TOXICITIES TO BE MONITORED AND DOSAGE MODIFICATIONS

This study will utilize the CTC (NCI Common Toxicity Criteria) Version 3.0 for toxicity and Adverse Event reporting. A copy of the CTC Version 3.0 can be downloaded from the CTEP home page (http://ctep.cancer.gov). All appropriate treatment areas should have access to a copy of the CTC Version 3.0.

8.A ESHAP Toxicities & Dose Modification

In the case of multiple toxicities, dose modifications should be based on the most severe dose-limiting toxicity.

8.A.1 Hematologic Toxicity:

The ESHAP regimen should be given as described in Section 7.A if the granulocytes are > 1,500 cells/ μ L and the platelets are > 100,000 cells/ μ L by the time the next cycle is due. If the blood counts have not recovered, treatment should be delayed by an additional week and counts repeated unless low peripheral counts are due to tumor. If, after 2 weeks, counts have not yet recovered, the patient should be treated at 75% of the last dose received of etoposide and cytarabine.

8.A.2 Grade 3 or 4 Infection:

(NCI Common Toxicity Criteria Version 3.0) due to chemotherapy-related neutropenia requires a decrease in the doses of etoposide and cytarabine to 75% of the last dose received. Re-escalation is at the discretion of the treating physician. In this study, filgrastim or peg-filgrastim may be administered to prevent neutropenia at the discretion of the treating physician.

The use of filgrastim or peg-filgrastim must be documented on the treatment flow sheets. Any toxicities associated with either of these agents must also be documented on the treatment flow sheets.

8.A.3 Impaired Renal Function:

All patients with serum creatinine levels ≤ 1.3 or creatinine clearance (CrCl) > 60 mL/min will receive full doses of all drugs. If the creatinine is 1.4-2.0 or the CrCl is 30-60 mL/min then the doses of cytarabine, etoposide, and cisplatin should all be reduced by 50%. A creatinine clearance of < 30 mL/min will require holding all treatment. Re-escalation to full dose is at the discretion of the treating physician if the serum creatinine level drops to ≤ 1.3 or the CrCl ≥ 50 mL/min.

TABLE 9 Cytarabine, Etoposide & Cisplatin Reductions According to Renal Function

CrCl	Etoposide Dose	Cytarabine Dose	Cisplatin Dose
-------------	-----------------------	-----------------	----------------

> 60 mL/min	100%	100%	100%
30-60 mL/min	50%	50%	50%
10-30 mL/min	0%	0%	0%
< 10 mL/min	0%	0%	0%

8.A.4 Neuropathy:

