13 STUDY ADMINISTRATION

13.A Review and Consent Requirements

13.A.1 Institutional Review Board (IRB)

The investigator will supply all necessary documents to be submitted to the IRB and will ensure that the institution has a properly structured research committee. The University of Arizona Human Subjects Protection Program will be the IRB of record. Documentation of initial and ongoing reviews, submission of serious adverse event reports, study amendments and revisions, and consent form modifications will be required. This documentation is to be forwarded to:

• Consent Forms:

[name]

Clinical Research Coordinator

The University of Arizona Cancer Center – North Campus

Room 2111

[name]

[name]

• Regulatory Documents:

[name]

Lymphoma Program Regulatory Coordinator

The University of Arizona Cancer Center, Room 1955

[name]

[name]

13.A.2 Patient Information and Informed Consent

Written informed consent will be obtained for this study from all patients. The investigator or his/her staff will explain the nature of the study and the risks involved to each patient prior to his/her inclusion in the trial. The patient will also be informed that he/she is free to withdraw from the study at any time. Original, signed informed consent forms for patients registered from the University of Arizona Cancer Center will be kept at The University of Arizona Cancer Center, North Campus, room 2111.

13.B Registration Procedure

All ethical, regulatory, technical, and scientific approvals must be in place before study registrations will accepted. All patients will be registered centrally with the Clinical Research Coordinator based at [contact] prior to the initiation of treatment. The Clinical Research Coordinator will assign each patient a sequential number prior to registration. The fully signed informed consent must be presented and all inclusion and exclusion criteria will be reviewed with the registering investigator or designee. All source documentation needed to confirm eligibility must be available for this review. A second phone registration is required prior to the initiation of Zevalin® to confirm eligibility and dose of therapy.

13.C Study Records - Data Collection & Recording

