APPENDIX A

STUDY CALENDAR

4/1/2010

STUDY CALENDAR Page 1

					Ibritumomab Tiuxetan (Zevalin)			
Required Studies	Baseline	ESH	AP Treatm	ent		Regin	nen [∞]	
Visits (weeks or days)	Within28 days prior to C1, D1	Cycle 1 Day 1	Cycle 2 Day1	Cycle 2 Day 29	Day 1	Day 2,3,4,5	Day 7, 8, or 9	Day 35
PHYSICAL								
History / Physical / vital signs ^α	X		X	X	ΧП			
Height / Weight / BSA / PS	X		X	X	ΧП			
Disease Assessment	X			X				
Toxicity Assessment	X		X	X	ΧП			
LABORATORY								
CBC / differential / platelets	X		X	X	ΧП			\mathbf{X}^{Σ}
Serum Creatinine / BUN	X		X	X	ΧП			
AST/ ALT/ Alk. Phos/ T. Bilirubin^	X							
LDH	X							
BHCG [†]	X							
Beta 2- microglobulin	X							
Hepatitis B screen*	X							
Pathology Review [£]	X							
Bone marrow cytogenetics [¥]	X			X				
Bone marrow aspiration and Bx	X			X				
SCANS								
CT or PET Chest	X			X				
CT or PET Abdomen	X			X				
CT or PET Pelvis	X			X				
Gamma Scan						X≠		
TREATMENT								
ESHAP		X	X					
Rituximab 250 mg/m2					X		X	
Ibritumomab Tiuxetan Indium (¹¹¹ In Zevalin)					X			
Ibritumomab Tiuxetan Ytrium-90 (90Y Zevalin)							X	

- α Vital Signs consist of BP, temperature and pulse
- t Baseline for women of childbearing potential
- ¥ A scan is performed at 48-72 hours after 111In Zevalin. Another optional scan may be performed at 90-120 hours after 111In Zevalin.
- ∞ ¹¹¹In Zevalin is administered 4-6 weeks after completion of ESHAP.
- ٨ Required at Baseline and Encouraged to repeat as clinically indicated by Good Medical Practice.
- Encouraged by Good Medical Practice, but not required.
- ¥ Bone Marrow cytogenetics can be done at either Baseline or C2,D29, but must be done at least once.
- £ Pathology Review consists of a basic review of a pathology report. If possible submit: Representative H&E stained slides from the diagnostic biopsy, one representative paraffin block and one copy of the pathology report.
- Σ Starting Day 35 (+/- 7 days) a CBC w/ Diff and Platelet count should be done every week until nadir.
- Within 28 days prior to Rituximab & Zevalin administration..

STUDY CALENDAR Page 2

Required Studies	Restaging	Short-Term Follow-Up				Long-Term Follow-Up	Off-Study [#]
Visits (weeks or days)	3 mos post ⁹⁰ Y Zevalin	6 mos post Zevalin	12 mos post Zevalin	18 mos post Zevalin	24 mos post Zevalin	Follow-Up: Annually for 3 years [£]	Disease Progression or Removed from Study (within 4 weeks)
PHYSICAL							
History / physical / vital signs ^α	X	X	X	X	X	X	X

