APPENDIX K Amendment #2 (4/27//07)

Summary of Changes

- Face Page: University of Arizona/Arizona Cancer Center Co-Investigators: deletion of [name]., and addition of [name]. (Medical Oncology); change of version date of the protocol to Amendment #2, April 27, 2007.
- Section 4.A. Inclusion Criteria: 4.A.1: Change in wording to indicate that patients may be in first, second, third, or fourth relapse (expanded from "first or second relapse". 4.A.9 Change in wording to "...Patients must have had at least 1, but no more than 4 prior chemotherapy regimens for lymphoma...."
- Section 5.B Evaluations During ESHAP Treatment and 5.C and 5.D Evaluations During postZevalin® follow-up and Appendix A: : Liver function tests (AST, ALT, alkaline phosphatase, total bilirubin), uric acid, glucose, and urinalysis will be obtained as clinically indicated, rather than required as part of the study. Restaging will occur 3 months (rather than 2 months) after completion of Zevalin®. Followup CT scans during the first 2 years after Zevalin® will be performed every 6 months, rather than every 3 months, unless clinically indicated. Thus, the revised CT schedule is at 6, 12, 18, and 24 months for 2 years and then every 6 months for 2 years, and then annually. The Zevalin® will be administered 4-6 weeks after completion of ESHAP (rather than 3-6 weeks). A required week 4 blood count after the Zevalin® treatment has also been added. The baseline anti-CD20 immunophenotyping in Appendix A has been deleted, as this will have been done as part of the original diagnostic testing before any treatment.
- Section 6.B and 6.C (Drug Information) and the Model Consent have been updated to include the new rituximab risk information received from the Study Sponsor and NCI (attached) for this study. The wording for the changes is that agreed upon by SWOG and the NCI for SWOG studies using rituximab or Zevalin® (which has ritiuximab as a component): revised wording regarding severe infusion and hypersensitivity reactions; new information on viral infections (including the possibility of progressive multifocal leukoencephalopathy related to JC virus), and gastrointestinal, cardiovascular, and renal toxicities; new cautions related to immunization, carcinogenesis, impairment of fertility, pregnancy, and nursing. APPENDIX H updated (Rituximab package insert 2/2007 update added).

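### Total bilirubin below 2.0 is a condition for Zevalin, but no bilirubin is required after baseline, so the check can rest on a value taken before both ESHAP cycles

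*Combined protocol and SAP*

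**What the plan says.** The note under 4.A.12 is specific to progression to Zevalin. It requires marrow involvement below 25% after the second ESHAP cycle, a platelet count that sets the 90Y dose, and "serum creatinine value < 2.0 and total bilirubin < 2.0". This is separate from the entry rule in 4.B.4, which excludes patients with bilirubin above 2.0 mg/dL.

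Section 13.B adds a checkpoint: "A second phone registration is required prior to the initiation of Zevalin® to confirm eligibility and dose of therapy". It names no laboratory test and no date window.

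Bilirubin is scheduled once, in the baseline panel of 5.A.4, within 28 days before Cycle 1 Day 1. At Cycle 2 Day 1 (5.B.2), Cycle 2 Day 29 (5.B.3) and Zevalin Day 1 (5.C.1), the chemistry line reads "Serum chemistries BUN, creatinine". In Appendix A the row for AST, ALT, alkaline phosphatase and bilirubin is marked in the Baseline column only, with the footnote "Required at Baseline and Encouraged to repeat as clinically indicated by Good Medical Practice".

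**The concern.** A mandatory condition for giving the radioimmunotherapy has no mandatory measurement at the time it applies. A patient whose bilirubin reached 2.0 or more during ESHAP could be registered to Zevalin if nobody chose to repeat the test.

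The protocol itself gives reasons to want a post-ESHAP value. Section 6.A.2 lists among the effects of cytarabine "chest pain, hepatic and renal dysfunction, and alopecia", and 6.A.3 mentions occasional hepatotoxicity with etoposide. The treatment that follows also irradiates the liver: the dosimetry summary in 1.D.2 gives a median absorbed dose from 90Y Zevalin of 450 cGy to liver, second only to spleen (742 cGy) among the organs listed.

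What is at stake is patient safety and a criterion that can be audited. The efficacy inference is not affected: under 4.C and 12.B, anyone who receives one dose of ESHAP is evaluable, whether or not Zevalin follows.

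**Working it through.** The plan gives no figure to reproduce. The check compares the conditions with the schedule and then counts days.

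**Conditions in the 4.A.12 note against required measurements after ESHAP starts**

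| Condition for Zevalin | Cycle 2 Day 1 | Cycle 2 Day 29 | Zevalin Day 1 |
|---|---|---|---|
| Marrow involvement | no | yes | no |
| Platelets | yes | yes | yes |
| Creatinine | yes | yes | yes |
| Total bilirubin | no | no | no |

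Section 5 and Appendix A agree on the bilirubin row, so a broken table does not explain the gap. Later visits do not fill it either: Day 35 is a blood count only, and restaging, follow-up and off-study chemistry is BUN, creatinine and LDH. The 28-day pre-Zevalin window in 5.C.1 applies only to the tests listed there, which omit bilirubin. Section 8.A has dose rules for counts, infection, renal function and neuropathy but none for liver function, so it does not prompt a repeat.

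**Age of the only required bilirubin**

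Inputs:
- Baseline draw 0 to 28 days before Cycle 1 Day 1 (5.A).
- Two 28-day cycles with infusions on Days 1 to 4 (Table 7). With Cycle 1 Day 1 as study day 1, Cycle 2 Day 1 is day 29, Cycle 2 Day 4 is day 32 and Cycle 2 Day 28 is day 56.
- Section 7.B: "The rituximab + ibritumomab tiuxetan regimen is given 4-6 weeks after completion of the second cycle of ESHAP", that is, 28 to 42 days.
- 90Y Zevalin on Day 7, 8 or 9 of that regimen, 6 to 8 days after its Day 1.

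The documents do not say whether completion means the last infusion or the end of the cycle, so both readings are shown. Minimum age = (earliest dosing day − 1) + 0. Maximum age = (latest dosing day − 1) + 28.

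*Reading A, completion on Cycle 2 Day 4 (day 32):*
- Zevalin Day 1 falls on day 32 + 28 = 60 to 32 + 42 = 74. Age: 59 to 73 + 28 = 101 days.
- 90Y falls on day 60 + 6 = 66 to 74 + 8 = 82. Age: 65 to 81 + 28 = 109 days.

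*Reading B, completion on Cycle 2 Day 28 (day 56):*
- Zevalin Day 1 falls on day 84 to 98. Age: 83 to 97 + 28 = 125 days.
- 90Y falls on day 90 to 106. Age: 89 to 105 + 28 = 133 days.

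Section 8.A.1 lets the second cycle slip: the rule that begins "If, after 2 weeks, counts have not yet recovered" implies a delay of up to 14 days for counts. The upper ages at 90Y become 109 + 14 = 123 days (A) or 133 + 14 = 147 days (B). These are not hard limits. The weekend and holiday allowance in 4.A.16, renal holds under 8.A.3 and repeat biodistribution imaging under 5.C.2 could each lengthen them. On every reading the value predates both cycles.

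**The case against.** The best reply is that the schedule is not the whole obligation. The note states a present requirement for progression, apart from the entry exclusion. Reading it as satisfied by the entry value would leave it almost no work to do, so it naturally means a current value. The visit lists are worded as minimum contents, Appendix A encourages repeats, and 13.B expects eligibility to be confirmed. History, examination and toxicity assessment are required before Zevalin, abnormal laboratory results must be appraised (section 9), and hepatitis B carriers are to be monitored (8.B.5). Any of these could prompt a repeat. The Amendment 2 summary also shows that the reduction was deliberate: liver tests "will be obtained as clinically indicated, rather than required as part of the study". Finally, the liver signal is thin. The cytarabine mention is one item in a long list, and 6.A.3 calls myelotoxicity the only clinically significant effect of etoposide.

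Much of this stands as mitigation. Many sites would probably repeat the test, and the number of patients harmed may be very small. But none of these provisions requires a bilirubin, and the hepatitis B provision covers only a subgroup. If the note does mean a current value, the schedule should include the test that supplies it. Leaving routine liver tests to clinical judgement is a reasonable choice; doing so while keeping a bilirubin threshold as a condition of treatment leaves the two provisions out of step.

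**Conclusion.** The point holds and is minor. Bilirubin is the only measured condition in the 4.A.12 note with no required value after ESHAP, and the gap applies to every patient who reaches Zevalin. The only required value is roughly two to four and a half months old at the 90Y dose (65 to 133 days across both readings, without delays). The schedule omission is clear from the text; the clinical consequence is not known, because the documents give no rate of bilirubin at or above 2.0 after ESHAP. The day counts rest on the two readings of ESHAP completion, but the conclusion does not. Sample size, error rates and the primary analysis set are unchanged.

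**What to change.** Add total bilirubin to the pre-Zevalin chemistry in 5.C.1 and mark it in the Zevalin Day 1 column of Appendix A, with the result available at the second registration in 13.B. The existing 28-day window would then apply. Since the regimen starts at least 28 days after ESHAP is completed, the value could not predate the last ESHAP infusion.

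Adding it at Cycle 2 Day 29 (5.B.3) would also give a post-ESHAP value. That visit is day 57, so the result would be 60 − 57 = 3 to 74 − 57 = 17 days old at Zevalin Day 1 under reading A, but 84 − 57 = 27 to 98 − 57 = 41 days old under reading B. Section 5.C.1 is therefore the tidier place.

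The cost is one extra analyte per patient on blood already being drawn, one line of text and one calendar mark. The downside is that some patients may fail the criterion and not receive Zevalin, which is what the criterion is for.
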